6.6. Dose Modification

6.6.1. Target Glucose Values for Titration of Insulin Therapy

The overall glycemic control goals for all participants enrolled in the study are similar to those recommended by the American Association of Clinical Endocrinologists (Bailey et al. 2016). Fasting, prandial, postprandial, and bedtime glucose target values used to reach the glucose goals and for determination of titration in insulin therapy are listed below.

Time of Target Glucose Measurement	Glucose Target (Range)
Fasting or Premorning meal	Target: 100 mg/dL or 5.6 mmol/L Range: 80 to <110 mg/dL or 4.4 to 6.1 mmol/L
Premidday meal	Target: 100 mg/dL or 5.6 mmol/L Range: 80 to <110 mg/dL or 4.4 to 6.1 mmol/L
Preevening meal	Target: 100 mg/dL or 5.6 mmol/L Range: 80 to <110 mg/dL or 4.4 to 6.1 mmol/L
Prebedtime	Range: 80 to <110 mg/dL or 4.4 to 6.1 mmol/L
1-2 hour or peak postprandial	Target: <140 mg/dL or 7.8 mmol/L

6.6.2. Basal Insulin Therapy and Titration

Participants must have been treated with basal insulin glargine U-100 prior to entering the study. Participants will continue their prestudy basal and prandial insulin therapy during the baseline period from Visit 2 to 4. The allowed basal insulin regimen during the study baseline and treatment periods is insulin glargine U-100 once or twice daily. The same dosing frequency should be maintained during the study.

The initial dose of basal insulin provided by the sponsor (insulin glargine U-100) at Visit 4 may be unit-for-unit. The basal insulin dose may be influenced by other clinical circumstances and

safety considerations known to the investigator; thus, the prescribed basal insulin dose during the study treatment period is determined by, and the responsibility of, the investigator.

The study basal insulin can be dosed at any time during the day and should be dosed at approximately the same time of day during study treatment. If there is a safety concern such as hypoglycemia, the dose timing of basal insulin may be changed per investigator discretion.

At all clinic and telephone visits during the 12-week treatment period, basal insulin dose should be reviewed and adjusted by the investigator, in discussion with the participant, based on CGM and hypoglycemia data. Twenty-four-hour glucose profiles from CGM should be evaluated for optimization of basal insulin dosing. Additional discussion between visits may be required to enable the participant to reach the glucose targets. Investigators may use discretion and provide direction for participants to adjust the basal insulin dose. Basal insulin should be titrated to reach the protocol target glucose values during the treatment period. Decreases to the basal insulin dose may be made at any time during the study based upon the judgment of the investigator (for example, in response to hypoglycemia). The participant should contact the site with any questions or concerns regarding insulin dosing.

Recommendations for basal insulin dose adjustment are described below. Hypoglycemia events can first be assessed over the previous week as described in the table below.

Hypoglycemic Events in the Previous Week	Basal Insulin Change
2 or more nocturnal hypoglycemia events occur or 1 severe hypoglycemia event occurs at any time of the day	Decrease the basal insulin dose to the previous lower dose (or by 10% if this is first dose).
1 nocturnal hypoglycemia event occurs	Do not increase basal insulin dose. Consider decrease in basal insulin dose if clinically indicated.
No nocturnal events occur	Titrate the basal insulin dose as described below.

After the hypoglycemia assessment, the fasting glucose CGM pattern over the previous 3 days can be used for basal insulin adjustment as described in the table below.

If fasting glucose CGM pattern is:	Adjust the basal insulin dose by:
<80 mg/dL (<4.4 mmol/L)	Decreasing dose to previous lower dose ^a
80-109 mg/dL (4.4-6.1 mmol/L)	No adjustment
110-129 mg/dL (>6.1-7.2 mmol/L)	Increasing by 1-2 units
130-149 mg/dL (>7.2-8.3 mmol/L)	Increasing by 2-4 units
150-179 mg/dL (>8.3-9.9 mmol/L)	Increasing by 4-6 units
≥180 mg/dL (≥10.0 mmol/L)	Increasing by 6-8 units

Abbreviations: CGM = continuous glucose monitoring.

^a If there is no previous dose because this was the first assigned dose, then the basal dose should be decreased by 10% in consultation with the investigator.

Source: Adapted from Bartley et al. 2008 and Bolli et al. 2009.

6.6.3. Study Prandial Insulin Therapy and Titration

Participants will continue their prestudy basal and prandial insulin therapy during the baseline period from Visits 2 to 4. At Visit 4, participants will start treatment with LY900014 and will administer their first study prandial insulin dose with the next meal following Visit 4. The total daily bolus insulin dose of LY900014 may be initiated unit-for-unit.

Study prandial insulin will be administered 0 to 2 minutes prior to the start of each meal (premorning meal, premidday meal, and preevening meal). Participants should follow a general daily pattern of administering prandial insulin doses with 3 main meals per day (morning, midday, and evening). Participants may have additional bolus insulin doses, such as with a snack, if clinically indicated.

This study will use 2 possible plans for determining prandial insulin dosing including:

- Carbohydrate-counting plan: If the participant performed flexible carbohydrate counting for prandial insulin dosing (insulin to carbohydrate ratio plan) prior to study enrollment, this plan may be continued during the study. The prandial insulin dose is based on the participant's estimated carbohydrate content of the meal (such as unit insulin per grams carbohydrate).
- Fixed-dose plan: The participant is prescribed a fixed dose or dose range of insulin for each meal. The fixed dose or dose range of insulin may be individualized for each meal.

The participant should maintain the same prandial insulin dosing plan throughout the study. Correction factor (for example, 1 unit of insulin per glucose [mg/dL or mmol/L] above target goal) may be implemented with either prandial insulin dosing plan.

Prandial insulin should be titrated to reach the protocol target glucose values during the treatment period. Decreases to the prandial insulin dose may be made at any time during the study based on the judgment of the investigator (for example, in response to hypoglycemia).

For participants who are using the carbohydrate-counting plan: the insulin to carbohydrate ratio (and correction factor if applicable) should be reviewed and adjusted by the investigator, in discussion with the patient, based on CGM and hypoglycemia data at all clinic and telephone visits during the 12-week treatment period. Twenty-four-hour glucose profiles, including premeal glucose and PPG levels, from CGM should be evaluated for optimization of prandial insulin dosing. Additional discussion between visits may be required to enable the participant to reach the glucose targets. The insulin to carbohydrate ratio may be adjusted every 3 days, or more often when appropriate, based on the participant's glycemic needs and glucose levels. Investigators may use discretion and provide direction for participants to adjust prandial insulin dosing. The participant should contact the site with any questions or concerns regarding insulin dosing.

For participants who are using the fixed-dose plan: A participant self-titration prandial insulin algorithm will be utilized as described below. At all clinic and telephone visits during the 12-week treatment period, prandial insulin dose (and correction factor if applicable) should be reviewed by the investigator in discussion with the participant based on CGM and hypoglycemia data. Twenty-four-hour glucose profiles, including premeal glucose and PPG levels, from CGM should be evaluated for optimization of prandial insulin dosing. Additional discussion between visits may be required to enable the participant to reach the glucose targets. The participant should contact the site with any questions or concerns regarding insulin dosing.

In the fixed-dose participant self-titration plan, assessment of the prandial insulin dose includes review of the previous day of CGM glucose values for the corresponding meal or bedtime as described in the table below. *For example, if assessing the need to adjust the morning meal prandial insulin dose, review the CGM glucose value from the previous day premidday meal.*

Prandial Insulin Dose Assessed	Corresponding CGM Glucose Value for Review
Fasting or morning premeal	previous day premidday meal glucose value
Midday premeal	previous day preevening meal glucose value
Evening premeal	previous day bedtime glucose value

Abbreviation: CGM = continuous glucose monitoring.

The CGM glucose value from the premeal or bedtime from the previous day is used by the participant as the "adjustment value" and the change in dose (either increase or decrease) is based upon this value as described in the table below.

CGM Glucose <80 mg/dL (<4.4 mmol/L)	CGM Glucose 80-109 mg/dL (4.4-6.1 mmol/L)	CGM Glucose >109 mg/dL (>6.1 mmol/L)
Decrease by 1 unit	No change	Increase by 1 unit

Abbreviations: CGM = continuous glucose monitoring.

Source: Adapted from Bergenstal et al. 2008 and Edelman et al. 2014.

For either prandial insulin dosing plan, the investigator may determine the appropriate correction factor for the participant to administer when premeal glucose levels are above target based on clinical judgment, taking into account the participant's clinical history with previous/current insulin regimen and recent glucose profiles. Alternatively, the correction factor may initially be calculated as follows:

correction factor = 1800/total daily insulin dose = estimated decrease in glucose (mg/dL) level per unit of prandial insulin administered, or

correction factor = 100/total daily insulin dose = estimated decrease in glucose (mmol/L) level per unit of prandial insulin administered

6.6.4. Transitioning off Study Prandial Insulin Therapy

Participants will take their last doses of study prandial insulin (LY900014) and study-provided basal insulin glargine prior to Visit 12 or at early discontinuation.

No special instructions for transition to nonstudy prandial insulin are necessary. The investigator, in consultation with the participant, will decide on the new prandial and basal insulin regimen, or other diabetes therapy, to be initiated.

6.7. Intervention after the End of the Study

LY900014 and basal insulin glargine will not be provided to participants after completion of the study treatment period. Prandial and basal insulins, as well as other diabetes therapies, are available for the treatment of T2D.

7. Discontinuation of Study Intervention and Participant Discontinuation/Withdrawal

7.1. Discontinuation of Study Intervention

Participants who need to discontinue from study treatment will also be discontinued from the study. Please refer to Section [7.2](#).

7.1.1. Temporary Discontinuation

During the study, participants who temporarily discontinue the IP may be able to resume the IP based on the following scenario:

The participant has not taken IP for 14 consecutive days or less:

- If the treatment regimen restarts within 14 days of when the participant initially stopped taking IP, the participant may continue in the study and begin treatment again with IP. During this time, nonstudy insulins may have been used. If the participant decides to continue in the study, no early termination procedures will be completed. Participants will continue study visits through the safety follow-up.

7.2. Participant Discontinuation/Withdrawal from the Study

Participants will be withdrawn from the study:

- at any time at his/her own request
- at the request of his/her designee (for example, parents or legal guardian)
- at the discretion of the investigator for safety, behavioral, compliance, or administrative reasons
- if participant has not taken IP for more than 14 consecutive days (see Section [7.1.1](#))
- if the participant becomes pregnant during the study
- if enrollment in any other clinical study involving an IP or enrollment in any other type of medical research judged not to be scientifically or medically compatible with this study
- if the investigator, after consultation with the sponsor-designated medical monitor, determines that a systemic hypersensitivity reaction has occurred related to study drug administration
- if the participant, for any reason, requires treatment with another therapeutic agent that has been demonstrated to be effective for treatment of the study indication, discontinuation from the study occurs prior to introduction of the new agent
- use of prohibited concomitant medication (see Section [6.5](#))

Discontinuation is expected to be uncommon.

At the time of discontinuing from the study, if possible, an early discontinuation visit should be conducted, as shown in the SoA. See SoA for data to be collected at the time of study discontinuation and follow-up and for any further evaluations that need to be completed. The participant will be permanently discontinued both from the study intervention and from the study at that time.

If the participant withdraws consent for disclosure of future information, the sponsor may retain and continue to use any data collected before such a withdrawal of consent. If a participant withdraws from the study, he/she may request destruction of any samples taken and not tested, and the investigator must document this in the site study records.

7.2.1. Discontinuation of Inadvertently Enrolled Participants

If the sponsor or investigator identify a participant who did not meet enrollment criteria and was inadvertently enrolled, then the participant should be discontinued unless there are extenuating circumstances that make it medically necessary for the participant to continue in the study.

If the investigator and the sponsor clinical research physician (CRP) agree it is medically appropriate to continue, the investigator must obtain documented approval from the sponsor CRP to allow the inadvertently enrolled participant to continue in the study. Safety follow-up is as outlined in Section 1.3 (Schedule of Activities), Section 8.2 (Safety Assessments), and Section 8.3 (Adverse Events and Serious Adverse Events) of the protocol.

7.3. Lost to Follow-up

A participant will be considered lost to follow-up if he or she repeatedly fails to return for scheduled visits and is unable to be contacted by the study site. Site personnel are expected to make diligent attempts to contact participants who fail to return for a scheduled visit or were otherwise unable to be followed up by the site.

8. Study Assessments and Procedures

- Study procedures and their timing are summarized in the SoA. Protocol waivers or exemptions are not allowed.
- Immediate safety concerns should be discussed with the sponsor immediately upon occurrence or awareness to determine if the participant should continue or discontinue study intervention.
- Adherence to the study design requirements, including those specified in the SoA, is essential and required for study conduct.
- All screening evaluations must be completed and reviewed to confirm that potential participants meet all eligibility criteria. The investigator will maintain a screening log to record details of all participants screened and to confirm eligibility or record reasons for screening failure, as applicable.

8.1. Efficacy Assessments

Primary Efficacy Assessments

The percentage and duration of time with sensor glucose values between 70 and 180 mg/dL (3.9-10.0 mmol/L) during the daytime hours.

Secondary Efficacy Assessments

The secondary efficacy measures in this study collected with CGM are

- change in HbA1c
- percentage and duration of time with sensor glucose values between 70 and 180 mg/dL (3.9-10.0 mmol/L) over 24 hours
- percentage and duration of time with sensor glucose values <54 mg/dL (<3.0 mmol/L) during daytime and 24-hour periods
- percentage and duration of time with sensor glucose values >180 mg/dL (>10.0 mmol/L) and >250 mg/dL (>13.9 mmol/L), during daytime and 24-hour periods
- incremental area under the glucose concentration-time curve from 0 to 1 hour, 0 to 2 hours after a meal

Other secondary efficacy measures in this collected in this study are

- proportion of participants with HbA1c $\leq 6.5\%$ and $<7.0\%$
- bolus, basal and total insulin dose (units and units/kg) and bolus/total insulin ratio
- change in Insulin Treatment Satisfaction Questionnaire (ITSQ) glycemic control domain score

8.1.1. Continuous Glucose Monitoring

The unblinded FreeStyle Libre 14-day CGM system will be used by all study participants from Visit 2 to Visit 12. This is an FDA-approved CGM system indicated for replacing blood glucose testing and detecting trends and tracking patterns aiding in the detection of episodes of hyperglycemia and hypoglycemia, facilitating both acute and long-term therapy adjustments in persons (age 18 and older) with diabetes.

Participants will use the:

- FreeStyle Libre sensor
 - The sensor can be worn for up to 14 days. Participants will be instructed to change the sensor according to the product information.
- FreeStyle Libre reader:
 - for participants to scan the sensor and for sites to upload CGM data to the CGM vendor
 - The reader also has a built-in blood glucose meter.
- LibreLink application (app) on a study-provided mobile device
 - for participants to scan the sensor and for sites to have remote access to CGM data for telephone visits and as clinically indicated
- Participants will be able to review CGM data for daily diabetes management with the reader and/or app.

Participants will receive training on the use of the system according to product information, and will be expected to complete the following study requirements:

- **Start each new sensor session with the reader first and then with the LibreLink app.**
- Change the sensor every 14 days or earlier if needed.
- Scan with the reader and app at least 4 times throughout the day (morning upon waking, prior to meals, bedtime) and as needed. After the start of a new sensor session, the sensor can be scanned with the reader and app in any order.
 - Make every effort to scan with the **reader and app** at least every 8 hours to avoid gaps in glucose data.
 - More frequent scanning is encouraged.
 - Participants should not ignore symptoms that may be due to hypoglycemia or hyperglycemia. Note that the FreeStyle Libre does not have alarms unless if the sensor is scanned.
- Participants should check sensor glucose readings with a blood glucose meter as instructed according to product information when the “Check Blood Glucose” symbol appears, when symptoms do not match sensor readings, or when readings are suspected to be inaccurate.

- The sensor must be removed before magnetic resonance imaging (MRI), computed tomography (CT) scan, X-ray, or diathermy treatment.
- Note and avoid substances that may interfere with sensor glucose readings including:
 - higher dose ascorbic acid (vitamin C) >1000 mg, which may raise sensor readings, and/or
 - salicylic acid (contained in some pain relievers such as aspirin) >650 mg, which may slightly lower sensor readings

8.2. Safety Assessments

Planned time points for all safety assessments are provided in the SoA (Section 1.3).

8.2.1. Physical Examinations

- A complete physical examination with measurement and record of height and weight.

8.2.2. Vital Signs

- For each participant, vital signs measurements should be conducted according to the SoA (Section 1.3).

8.2.3. Electrocardiograms

- Single 12-lead electrocardiograms (ECGs) will be obtained as outlined in the SoA (see Section 1.3) using an ECG machine that automatically calculates the heart rate and measures pulse rate, QRS, QT, and corrected QT intervals.

8.2.4. Clinical Safety Laboratory Assessments

- See Appendix 2 (Section 10.2) for the list of clinical laboratory tests to be performed and the SoA for the timing and frequency.
- The investigator must review the laboratory report, document this review, and record any clinically relevant changes occurring during the study in the AE section of the case report form (CRF). The laboratory reports must be filed with the source documents. Clinically significant abnormal laboratory findings are those which are not associated with the underlying disease, unless judged by the investigator to be more severe than expected for the participant's condition.
- All laboratory tests with values considered clinically significantly abnormal during participation in the study should be repeated until the values return to normal or baseline or are no longer considered clinically significant by the investigator or medical monitor.
 - If such values do not return to normal/baseline within a period of time judged reasonable by the investigator, the etiology should be identified and the sponsor notified.
 - All protocol-required laboratory assessments, as defined in Appendix 2 (Section 10.2) and Appendix 5 (Section 10.5), must be conducted in accordance with the laboratory manual and the SoA.

- If laboratory values from non-protocol-specified laboratory assessments performed at the institution's local laboratory require a change in participant management or are considered clinically significant by the investigator (for example, SAE or AE or dose modification), then the results must be recorded in the CRF.

8.2.5. Hypoglycemia

Participants will use unblinded CGM for diabetes management. Participants should check sensor glucose readings with a blood glucose meter as instructed (also refer to Section 8.1.1).

Participants will be instructed to treat glucose <70 mg/dL (<3.9 mmol/L) as hypoglycemia. The participant should contact the site as necessary.

Hypoglycemia will be described using the following definitions :

- **Level 1** hypoglycemia: glucose <70 mg/dL (3.9 mmol/L) and \geq 54 mg/dL (3.0 mmol/L) as assessed by CGM
- **Level 2** hypoglycemia: glucose <54 mg/dL (<3.0 mmol/L) as assessed by CGM
- **Level 3: Severe Hypoglycemia:** A severe event characterized by altered mental and/or physical status requiring assistance for treatment of hypoglycemia. Participants have altered mental status and cannot assist in their own care, may be semiconscious or unconscious, or experience coma with or without seizures, and require assistance of another person to actively administer carbohydrate, glucagon, or other resuscitative actions. Glucose measurements may not be available during such an event, but neurological recovery attributable to the restoration of blood glucose concentration to normal is considered sufficient evidence that the event was induced by a low blood glucose concentration.
 - The determination of a hypoglycemic event as an episode of severe hypoglycemia, as defined above, is made by the investigator based on the medical need of the participant to have required assistance and is not predicated on the report of a participant simply having received assistance.
 - All episodes of severe hypoglycemia must be reported as serious on the AE eCRF page and on the SAE eCRF page. Episodes of hypoglycemia not meeting the criteria for severe hypoglycemia should not be reported as an AE.

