10.3.1. Definition of AE

AE Definition

- An AE is any untoward medical occurrence in a patient or clinical study participant, temporally associated with the use of study intervention, whether or not considered related to the study intervention.
- NOTE: An AE can therefore be any unfavorable and unintended sign (including an abnormal laboratory finding), symptom, or disease (new or exacerbated) temporally associated with the use of study intervention.

Events Meeting the AE Definition

- Any abnormal laboratory test results (hematology, clinical chemistry, or urinalysis) or other safety assessments (for example, ECG, radiological scans, vital signs measurements), including those that worsen from baseline, considered clinically significant in the medical and scientific judgment of the investigator (that is, not related to progression of underlying disease).
- Exacerbation of a chronic or intermittent preexisting condition including either an increase in frequency and/or intensity of the condition.
- New conditions detected or diagnosed after study intervention administration even though it may have been present before the start of the study.
- Signs, symptoms, or the clinical sequelae of a suspected drug-drug interaction.
- Signs, symptoms, or the clinical sequelae of a suspected overdose of either study intervention or a concomitant medication. Overdose per se will not be reported as an AE/SAE unless it is an intentional overdose taken with possible suicidal/self-harming intent. Such overdoses should be reported regardless of sequelae.
- “Lack of efficacy” or “failure of expected pharmacological action” per se will not be reported as an AE or SAE. Such instances will be captured in the efficacy assessments. However, the signs, symptoms, and/or clinical sequelae resulting from lack of efficacy will be reported as AEs or SAEs if they fulfill the definition of an AE or SAE.

Events NOT Meeting the AE Definition

- Any clinically significant abnormal laboratory findings or other abnormal safety assessments which are associated with the underlying disease, unless judged by the investigator to be more severe than expected for the participant’s condition.
- The disease/disorder being studied or expected progression, signs, or symptoms of the disease/disorder being studied, unless more severe than expected for the participant’s condition.

- Medical or surgical procedure (for example, endoscopy, appendectomy): the condition that leads to the procedure is the AE.

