10.3.2. Definition of SAE

If an event is not an AE per definition above, then it cannot be an SAE even if serious conditions are met (for example, hospitalization for signs/symptoms of the disease under study, death due to progression of disease).

A SAE is defined as any untoward medical occurrence that, at any dose:

a. Results in death

b. Is life-threatening

The term “life-threatening” in the definition of “serious” refers to an event in which the participant was at risk of death at the time of the event. It does not refer to an event, which hypothetically might have caused death, if it were more severe.

c. Requires inpatient hospitalization or prolongation of existing hospitalization

- In general, hospitalization signifies that the participant has been admitted to hospital for observation and/or treatment that would not have been appropriate in the physician’s office or outpatient setting. Complications that occur during hospitalization are AEs. If a complication prolongs hospitalization or fulfills any other serious criteria, the event is serious. When in doubt as to whether “hospitalization” occurred or was necessary, the AE should be considered serious.
- Hospitalization for elective treatment of a preexisting condition that did not worsen from baseline is not considered an AE.

d. Results in persistent disability/incapacity

- The term disability means a substantial disruption of a person’s ability to conduct normal life functions.
- This definition is not intended to include experiences of relatively minor medical significance such as uncomplicated headache, nausea, vomiting, diarrhea, influenza, and accidental trauma (for example, sprained ankle) which may interfere with or prevent everyday life functions but do not constitute a substantial disruption.

e. Is a congenital anomaly/birth defect

f. Other situations:

- Medical or scientific judgment should be exercised in deciding whether SAE reporting is

appropriate in other situations such as important medical events that may not be immediately life-threatening or result in death or hospitalization but may jeopardize the participant or may require medical or surgical intervention to prevent 1 of the other outcomes listed in the above definition. These events should usually be considered serious.

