6.9.3. Hypoglycemic Events

Only severe hypoglycemia will be collected as AEs and all episodes of severe hypoglycemia will be considered as SAEs. Severe hypoglycemia rates and incidence during the treatment period (Visits 4-12) will be summarized.

A listing of patients with at least 1 severe hypoglycemia reported (as SAE) after Visit 4 (including Visit 801) will be provided.

A list of MedDRA PTs will be used for the narrow search of potential severe hypoglycemia in spontaneously reported AEs. The events identified through the search strategy that are also reported as SAEs will be summarized.

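### Protocol 8.2.5 bars AE reporting of all hypoglycemia below Level 3, with no exception for serious or treatment-ending episodes, and so conflicts with the AE definition in Appendix 3

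*Protocol*

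**What the plan says.** Protocol 8.2.5 sorts hypoglycemia into three levels. Levels 1 and 2 are defined by CGM glucose alone; Level 2, for example, is "hypoglycemia: glucose <54 mg/dL (<3.0 mmol/L) as assessed by CGM". Level 3 (severe) rests on altered status with a need for help from another person, and that determination "is made by the investigator based on the medical need of the participant to have required assistance".

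Reporting then splits at Level 3. Above the line: "All episodes of severe hypoglycemia must be reported as serious on the AE eCRF page and on the SAE eCRF page". Below it: "Episodes of hypoglycemia not meeting the criteria for severe hypoglycemia should not be reported as an AE". SAP 6.9.3 restates the split, saying that severe hypoglycemia is the only hypoglycemia collected as an AE. It adds a MedDRA preferred-term search of spontaneously reported AEs, of which: "The events identified through the search strategy that are also reported as SAEs will be summarized".

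Appendix 3 is written without reference to this split. Protocol 10.3.1 gives a general AE definition and lists among qualifying events: "Signs, symptoms, or the clinical sequelae of a suspected overdose of either study intervention or a concomitant medication". Protocol 10.3.2(c) gives as a seriousness criterion: "Requires inpatient hospitalization or prolongation of existing hospitalization". Protocol 10.3.2 also opens with a filter: if an event is not an AE under the definition that precedes it, "then it cannot be an SAE even if serious conditions are met".

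**The concern.** Level 3 measures the need for assistance. It does not measure seriousness in the regulatory sense, and the two can part. Take a hypothetical participant who injects too much insulin by mistake, falls to 45 mg/dL, stays alert, self-treats, and is admitted overnight for observation. Another might leave the study because of repeated Level 2 lows. Neither need meet Level 3.

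Hypoglycemia is a central risk when insulin is titrated to glucose targets. The trial is open-label and single-arm and has no data monitoring committee, so individual serious-event reports carry much of the safety signal. A rule that keeps some serious or treatment-ending episodes off the AE page would remove them from expedited reporting and from the event-based tables. Two sections that point in different directions also leave sites free to handle the same case differently.

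**Working it through.** No figure in the plan bears on this point, so the check sets the texts side by side and then traces an episode through the outputs.

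**Texts side by side**

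| Question | Protocol 8.2.5 and SAP 6.9.3 | Protocol 8.3.1, 8.4 and Appendix 3 |
|---|---|---|
| Is hypoglycemia below Level 3 an AE? | Not reported as one; no exception | 10.3.1 is general and has no hypoglycemia carve-out. It includes overdose sequelae, and 8.4 links excess insulin to hypoglycemia |
| Does hospital admission matter? | Not mentioned | 10.3.2(c): it makes an AE serious, and admission for observation counts |
| Does discontinuation matter? | Not mentioned | 8.3: the investigator must follow AEs that led to discontinuation |
| What must be recorded? | Level 3 only | 8.3.1: every AE after consent, each assessed for seriousness |

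The opening filter of 10.3.2 does not settle the matter. It refers back to the definition in 10.3.1, not to 8.2.5, and 10.3.1 does not exclude hypoglycemia. The direct conflict is therefore between 8.2.5 and the AE definition in 10.3.1. The conflict with the hospitalization criterion follows from it.

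**Tracing an episode if 8.2.5 is followed**

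| Output | Level 3 episode | Below Level 3, admitted or treatment-ending |
|---|---|---|
| AE page | Yes | No |
| SAE page and 24-hour report (Protocol 8.3.1) | Yes | No |
| SAE table (SAP 6.9.2) | Yes | No |
| AE-discontinuation table (SAP 6.9.2) | Yes, if it ends treatment | No |
| Severe-hypoglycemia rates and incidence (SAP 6.9.3) | Yes | No, by definition |
| Narrative (SAP 6.9.6) | Yes, as an SAE | Not triggered by the episode |
| MedDRA search (SAP 6.9.3) | Yes, if coded to a listed term | No; the search starts from reported AEs |
| Disposition summary and listing (SAP 6.3) | Yes, if discontinued | Yes, if discontinued, but not as an AE |
| CGM time below range (SAP 6.10) | As minutes, within analyzed windows | As minutes, within analyzed windows |

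**How far CGM fills the gap**

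CGM time below range counts minutes, not consequences. SAP 6.10.1 analyzes it after baseline in three 2-week windows (Weeks 2-4, 6-8 and 10-12), which is 3 x 2 = 6 of the 12 treatment weeks. Weeks 0-2, straight after the switch to study insulin, lie outside the windows. Days with less than 70% of the 96 expected readings are dropped; 0.70 x 96 = 67.2, so a day needs at least 68.

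**The case against.** The strongest reply is that this is a deliberate and visible design. Lows at Levels 1 and 2 are handled by CGM, and AE pages are kept for Level 3. Percent time below 54 mg/dL is a named secondary endpoint. The SAP adds percent and minutes below 54, below 70 and from 54 to below 70 mg/dL, by day, night and 24 hours, as well as postprandial hypoglycemia. Level 3 events are always SAEs and are summarized, listed and narrated. All this stands. A reader might infer that the plan hides the main harms of insulin from its safety tables; the documents do not support that.

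A second reply is that the specific rule in 8.2.5 governs, so that the 10.3.2 filter makes the whole consistent. That reading is possible, which is why a flat contradiction with the SAE definition would be too strong a claim. But the filter cites 10.3.1, and nothing there yields to 8.2.5. One could also point to the 10.3.1 exclusion for expected signs of the disease under study. Protocol 8.4, however, ties hypoglycemia to excess insulin, and that exclusion itself gives way when the event is worse than expected. The overdose bullet reaches only episodes that follow a suspected overdose; for the rest, the conflict rests on the general AE definition.

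Third, other routes exist. Withdrawals and their reasons are summarized and listed under SAP 6.3. Immediate safety concerns go to the sponsor under Protocol 8. A separate consequence such as an injury is not excluded by 8.2.5 and stays reportable. These routes narrow the gap, but none is an AE or SAE record of the episode.

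Fourth, a reader might infer that the MedDRA search can surface no misclassified case. That is too absolute: it could still find an SAE coded to a listed term but not identified as severe hypoglycemia. It cannot recover an episode that was never entered as an AE.

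**Conclusion.** The point holds in a limited form. Protocol 8.2.5 and SAP 6.9.3 exclude all hypoglycemia below Level 3 from AE reporting without a seriousness or discontinuation exception. This conflicts with 10.3.1 and, through it, with 10.3.2(c).

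What is lost is event-level AE/SAE reporting, expedited notification, narratives and AE-discontinuation entries for serious or treatment-ending episodes below Level 3. Level 3 reporting, the CGM endpoints and the disposition counts are unaffected.

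The size cannot be computed. The documents give no rate for such episodes, and many admitted cases may meet Level 3 through the need for assistance. Any case count would be an assumption, so none is offered. The conclusion assumes only that such an episode can occur and that sites follow 8.2.5 as written. Whether sites would in fact divide between the two texts cannot be known from the documents, but the texts permit it. The change is worth making because it costs little and the omission concerns serious-event reporting.

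**What to change.** Reconcile the passages as follows.

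- **Protocol 8.2.5, last sentence:** add an exception to this effect: unless the episode meets a criterion in 10.3.2 or leads to discontinuation of IP or study, in which case it is reported as an AE, and as an SAE where a 10.3.2 criterion is met.
- **SAP 6.9.3:** mirror the exception in the sentence that limits AE collection to severe hypoglycemia.
- **eCRF:** add a Level 3 yes/no flag, and use it to define the severe-hypoglycemia rates, incidence and listing. At present a hypoglycemia SAE reported under 8.2.5 is by construction a Level 3 event. After the change it need not be, and the flag keeps the endpoint as it is.

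The cost is one protocol sentence by amendment, the matching SAP text, one eCRF field, and a few extra AE or SAE reports with their narratives. No efficacy analysis and no treatment rule changes. There is no need to query every non-serious hit from the MedDRA search.
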